**Data Collection:**

Subjects will have the options of completing study surveys/questionnaires online via email link to REDCap prior to study visit. If not completed by the time the study visit takes place, the coordinator can provide the iPad digital version of the survey/questionnaire to the subject for the in-person visits or can interview the patient via phone for the telephone visits. Data Collection in this study will utilize REDCap. All other data collection will be entered directly into this password protected system.

**Assessments:**

*Safety:*

- PRIME-MD Questionnaire: A validated and frequently used self-report measure of depressive symptoms comprising of 2 questions, which were derived from the PHQ.

### Outcomes:

- **Demographics Form:** This form collected demographic and other lifestyle history of the research subject.
- **Burnout:** We will measure burnout using 2 single-item measures adapted from the full Maslach Burnout Inventory (MBI). These 2 items have been demonstrated to correlate strongly with the emotional exhaustion and depersonalization domains of burnout measured by the full MBI in a sample of over 10,000 individuals with an area under the ROC curve of 0.94 and 0.93 for emotional exhaustion and depersonalization, respectively, for these single items relative to the full MBI.
- **Quality of Life:** Will be measured using the *Linear Analogue Self-Assessment (LASA)*. This measure is a six-item measure of quality of life (QOL), in which QOL is conceptualized as a multidimensional construct with five domains (physical, functional, emotional, spiritual, and social). This data will be collected at screen (prior to any treatment), day 14, day 30, day 60, end of treatment day 90, and at end of study day 180 (3months post last treatment).
- **Stress:** Will be evaluated through the *Perceived Stress Scale (PSS)*. The PSS is a 10-item Likert scale that measures global life stress by assessing the degree to which experiences are appraised as uncontrollable or unpredictable. Scores can range from 0 to 40, with higher scores indicating greater perceived stress. Reliability is reported as 0.85, with Cronbach alphas ranging from 0.75-0.86.
- **Resilience:** Will be evaluated through the *Connor-Davison Resilience Scale 10 (CD-RS10)*. This is a 10-item, likert scale, validated, scoring system. The CD-RS10 is a reliable means of assessing resilience and most often used in medical and/or disaster studies.
- **Sleep Quality:** *The Pittsburgh Sleep Quality Index (PSQI)* is an effective instrument used to measure the quality and patterns of sleep in adults. This is a 9-item, likert scale, validated, scoring system. It differentiates “poor” from “good” sleep quality by measuring seven areas (components): subjective sleep quality, sleep latency, sleep duration, habitual sleep efficiency, sleep disturbances, use of sleeping medications, and daytime dysfunction over the last month.
- **Cognitive Testing:** *The Cambridge Brain Science (CBS)* web-based tests were developed in the laboratory of [name], Canada Excellence Research Chair in Cognitive Neuroscience and Imaging (owenlab.org), over the course of his 25-year career. The tests are self-administered, do not require supervision, and effectively assess aspects of cognition including reasoning, memory, attention and verbal ability. Over 300 scientific studies have been run to date using the CBS tests, yielding numerous publications in leading academic journals. The tests have been validated in studies of patients, brain imaging studies of healthy volunteers and in several large-scale public studies involving tens of thousands of volunteers. They have proven to be efficient and sensitive measures of cognitive performance and can be used to consistently monitor participants and patients due to the unlimited versions of problem sets within each task. The 12 tasks (\*see CBS Task Overview.pdf) can be customized to use specific tasks if a shortened assessment is required for research. A custom 3-task assessment would take approximately 10 minutes and for the purposes of this study, we would recommend the use of the following tasks:
  - 1) **Double Trouble** – 90 seconds (*measure of Response Inhibition*) - Version of the Stroop task. It is a “double” version in which there can be up to two incongruities (the top word and the bottom words), so is a little more difficult than other versions and has been sensitive to a range of interventions known to improve attention, response inhibition, or cognition in general. Response times and accuracy can be separately calculated for each difficulty level (congruent /incongruent / double incongruent), in addition to an overall score.

- 2) **Feature Match** – 90 seconds (*measure of Attention*) - Version of a “spot the difference” game. It uses areas of the brain involved in tuning attention and requires both fast response time and accuracy to get a good score.
  - 3) **Grammatical Reasoning** – 90 seconds (*measure of Verbal Reasoning*) - Based on Alan Baddeley’s grammatical reasoning test (Baddeley, 1968). Short sentences describing the relationship of two shapes along with an image of the shapes are displayed on the screen. Participants must indicate whether the sentence correctly describes the pair of objects displayed on the screen.
- **Satisfaction with the program:** This questionnaire is adapted from *Was it Worth it Questionnaire (WIWI)* to measure study and Muse-S™ satisfaction. It will be administered to the participants after completing the intervention at the end of the study, probing their satisfaction with the research study. These data could be used to assess the feasibility of the intervention by asking the patient if the entire research experience was worth it for them.

*Adherence to Intervention:*

- **Adherence to the Muse-S™** will be assessed by de-identified data available within the cloud, provided by InteraXon. InteraXon only has information per subject through subject ID only (as was provided by Mayo Clinic site), so when the cloud data is provided to Mayo, it will be linked to each subject through their study ID.

*Intervention:*

- **The Muse-S™ Headband system:** The Muse-S™ Headband system is a brain sensing headband that measures brain activity by detecting electrical impulses created by the brain. The Muse-S™ Headband system uses a series of focus attention training methods to train the brain. Each focus attention session can vary in length, with the ideal being a minimum of 10 minutes, and has been shown to reduce stress, anxiety, and improve focus and productivity. The Muse-S™ Headband system has seven sensors with four channels of EEG data for an accurate, high-quality experience. The battery life is approximately five hours and uses an industry-standard micro-USB charger. Twenty Muse-S™ Headband systems will be provided by the manufacturer at no cost in support of this study.

[figure not shown]
Use of Muse-S™ Headband systems will be demonstrated to each participant prior to their first mindfulness practice session, which will be completed during the baseline visit with the study coordinator. The study coordinator will present the participant with detailed instructions on how to begin each session. The frequency of the sessions thereafter will be at the participant’s discretion according to the study’s requirements (daily practice). Mindfulness training will follow the protocol in the Muse-S™ APP, which follows a standard breathing exercise with EEG brain state feedback through the mobile device, as designed by a panel of experienced mindfulness practitioners. In short, the Muse-S™ is a *FitBit* like device for the brain.

The study participants can access 3 different types of meditation while using the Muse-S™ Headband system. They are as follows:

- **Mind Meditation** uses the Muse-S™ headband to track the user's brain activity during meditation and translates the brain's activity into guiding sounds. Users get real time feedback to know when their mind is focused and when it's distracted, and are cued to return to a state of focused attention (meditation state). Users also see data from their brain after the meditation. Real time feedback during Mind Meditation is the Muse-S™ signature meditation and teaches the fundamentals of a meditation practice-remaining in a calm focused attention state and being able to move your mind away from distracting thoughts.
- **Guided Meditations from Healthcare Burnout Collection.** Guided meditations are narrated meditations on a range of subjects like stress, focus, breath and body practices. We will put together a collection of meditations specifically for HCP. Guided meditations can be done with or without the Muse-S™ headband. When they are done with the headband, there is no real-time feedback, but you see data from your brain, heart and movement after the session. You are welcome to do guided sessions without the headband.
- **Go-to-sleep Meditations** use the headband and are guided meditations that can be combined with an audio sound scape generated from your biosignals (heart rate, brain and movement). Sleep Journeys are designed to help you fall asleep faster. They are intended to be used in bed while you fall asleep to help calm your body and mind and entrain you into sleep. If you fall asleep with the headband on you can wear it through the night if you wish. Some people find Go-to-sleep journeys deeply relaxing and use them during the day as a relaxation tool as well.

All study participants will have access to The Muse-S™ Headband system’s customer service team based in Toronto, Canada, by telephone and email for assistance should they experience technical problems with the device.

- **Server Data:** As the subject completes any Muse-S™ sessions, the information from these sessions will be uploaded to the Muse-S™ iCloud servers hosted by Google. Each subject will be able to see their own data at the end of each session, and data from the previous session stored in the “me” tab in the app. Subject to the study organizers ensuring that the subjects have signed the appropriate consents, study organizers will have access to each subject’s data to monitor compliance, performance and outcomes, but will not get access to Journal entry information (if subject chooses to write a Journal entry). These data that the study organizers will have access to can include the study-specific identification number, gender, and age of the subject, the session type, the time and duration of each session, EEG data, heart rate (PPG) data, and the performance per session. Interaxon’s privacy policy, which can be found at [www.choosemuse.com/privacy](http://www.choosemuse.com/privacy) will apply to Interaxon’s use of the subjects’ data. In order to maximize protection of the individual’s privacy, the study organizers will ensure that the subjects

are assigned anonymized email address and names for use in the Muse -S™ application and when contacting the Muse-S™ customer support. To ensure that no health data is shared with Interaxon, the study organizers have agreed to ensure that no health data will be shared with Interaxon. At the end of the study, the data collected in Google ICloud Server associated with study email addresses will be deleted.

- The Muse-S™ steps include: 1) Open the Muse-S™ App on your phone. 2) select meditation type 3) if meditating with the headband, turn on the Muse-S™ headband. It will pair via bluetooth to the app 4) put on headband (if doing a meditation with headband) 5) meditate 6) add any journal or mood entry if desired 7) review results
- Cleaning the Muse-S™: Each patient will be given a brand new, out-of-the-box Muse-S™ Headband system. If cleaning must occur, the entire Muse-S™ including the head set can be wiped down with a standard disinfectant wipe. The band can also be hand-washed gently with soap and water. The module on the band is not waterproof but can be wiped with disinfectant.

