**Study Design and Methods**

**Methods:**

All study participants will receive the Muse S™ Headband system at study entry and will be asked to utilize it at least 4 times per week for a minimum of 10 minutes each time over a period of 3 months (12 weeks). They will be followed for a period of 6 months (3 months of treatment and 3 months post treatment) according to the schedule below.

We will assess the following:

- Type of meditation the patient has selected from the 3 available options: Mind Meditation, Guided Meditation and Go-to-sleep meditation.
- Frequency and duration of use from baseline to month 3 (end of treatment). The participants will be informed at baseline that for best results, it will be recommended that they use it a minimum of 10 minutes, at least 4 times per week for over 3 months. If they are short on time, they can break up the 10 minutes and do shorter meditations.

- Changes in QOL, stress, resilience, and sleep score from baseline through week 2, month 1, month 3 and month 6.

Visit No.	Consent /screen /baseline	Treatment Phase			Follow up Phase
	1	2	3	4	5
Visit Type	face to face	Phone/ email	Phone/ email	face to face/phone/ email	face to face/phone/ email
Visit Days	0	14	30	90	180
Informed Consent	X				
Inclusion/Exclusion	X				
Demographic and History Form	X				
Depression	X	X	X	X	X
Burnout	X			X	X
Resilience	X	X	X	X	X
Sleep	X	X	X	X	X
Quality of Life	X	X	X	X	X
Stress Scale	X	X	X	X	X
Satisfaction Survey					X
Adverse Events 		X	X	X	X
CBS Cognitive Tests	X			X	X
Concomitant Medication 	X	X	X	X	X
Instructions for Muse-S™	X				
End of Treatment/End of Study Forms				X	X

1 = For visit 5, only serious adverse events will be newly collected; 2 = For visit 5, only newly added concomitant medications will be collected

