#### **Subject Retention:**

Participants will not be remunerated for participating in this study, but they will be allowed to keep the Muse-S™ Headbands.

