#### **Resources:**

- The data entry screens used will be developed via REDCap for the online forms.
- Clinician investigators will provide medical oversight.
- The Muse-S™ Headband systems are provided at no cost through the manufacturer (InteraXon) for use during study participation.

Check all that apply. If none apply, leave blank:

The research involves contact or interaction with subjects, for example, surveys, questionnaires, observation, blood draw.

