#### Recruitment:

HCP participants will be recruited from the Mayo Clinic Practice. The study staff will inform participants of the study during practice meetings, and if the participants indicate interest they will connect with research staff and arrange a time to meet to begin the consent process.

Participants will not be reimbursed for their time spent in the study, but all participants will be given the option of keeping the Muse-S™ Headband system for continued use post study participation.

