**Subject Information**

**Target accrual:** We plan to recruit 40 Mayo Clinic Practicing HCP.

**Subject population:** A total of 40 practicing HCP at Mayo Clinic who meet the following study criteria:

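### Does a stated supply of twenty headbands undermine the planned accrual of 40?

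*Protocol*

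**What the plan says.** The Protocol gives the number of participants twice under Subject Information. Target accrual reads "We plan to recruit 40 Mayo Clinic Practicing HCP", and the subject population is "A total of 40 practicing HCP at Mayo Clinic who meet the following study criteria".

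On devices, the Methods section says "All study participants will receive the Muse S™ Headband system at study entry". The cleaning instructions add that "Each patient will be given a brand new, out-of-the-box Muse-S™ Headband system". Two sections deal with what happens afterwards. Subject Retention says of participants that "they will be allowed to keep the Muse-S™ Headbands", and Recruitment says that "all participants will be given the option of keeping the Muse-S™ Headband system for continued use post study participation".

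Supply is mentioned in two places. The paragraph describing the headband system says "Twenty Muse-S™ Headband systems will be provided by the manufacturer at no cost in support of this study". The Resources section says "The Muse-S™ Headband systems are provided at no cost through the manufacturer (InteraXon) for use during study participation" and gives no number.

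The SAP does not mention device supply. It plans descriptive statistics for frequency and duration of use, and linear mixed models for the questionnaire and cognitive outcomes. It calls all analyses exploratory. Neither document gives a power or precision calculation for the 40.

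**The concern.** One new device per person and 40 people make 40 devices, and the only count in the documents is half of that. The usual ways to stretch a short supply are closed: a returned unit cannot go to a later participant if each must be new, and participants may keep theirs anyway.

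If twenty really were the limit, enrolment could stop at half the target. Feasibility would then be described in 20 people instead of 40, and every interval would be wider. Aim 2 also depends on the device, because active-state and calm-state durations are recorded only by the headband. Since nothing in the documents justifies 40 statistically, no derivation is available to show which of the two figures is current.

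**Working it through.** **Inputs**
- Planned participants: 40 (Protocol, Subject Information, stated twice).
- Devices per participant: 1, new, given at entry (Protocol, Methods and the cleaning instructions).
- Devices returned for reuse: none can be relied on (Protocol, Subject Retention and Recruitment).
- Devices with a stated count: 20 (Protocol, description of the headband system).
- Further supply: no number and no limit (Protocol, Resources).

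**The count.** Neither 20 nor 40 is derived in the documents, so there is no calculation to reproduce. The comparison is direct:
- Devices needed = 40 × 1 = 40, before any spares.
- Without a stated supply = 40 − 20 = 20.
- Share covered by the stated count = 20 / 40 = 50%.

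**Can the text close the gap?**
- Reuse: no. It conflicts with a new unit for each person and with the option to keep it.
- Taking part without a headband: no. Guided sessions may be done without it, but Methods still gives a device to everyone.
- A second supplier: none is named.
- More units from the same manufacturer: not excluded. The sentence with the count does not present twenty as a total, and Resources attributes the systems to the manufacturer without restricting the number.

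The figures are therefore unreconciled, but they are not strictly contradictory.

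**What a cap would cost, if there were one.** Assume that supply stops enrolment at 20 and that data are complete. For a simple mean change, the 95% half-width in SD units is t(0.975, n−1)/√n:
- n = 40: 2.023 / 6.325 = 0.32.
- n = 20: 2.093 / 4.472 = 0.47.
- Ratio of standard errors: √(40/20) = 1.41.

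These figures depend entirely on the assumed cap. They describe a simple mean, not the SAP's mixed models, and the plan sets no precision target to judge them against. With 40 devices the ratio is 1 and nothing changes.

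**Does the analysis use the device count?** No. The primary summary uses frequency and duration of use, the stress and sleep model uses time spent with the device, and the other models estimate change over time. Each runs on whoever is enrolled.

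**The case for a change.** The strongest case for acting is that both numbers stand in current text, the mismatch is a factor of two, and one corrected figure or one added sentence would remove it. Read together, Resources names the manufacturer as the only source and the intervention paragraph puts its contribution at twenty. An unstated possibility of more units does not reconcile the written figures. A device study whose first aim is feasibility of use should also be able to show that it can equip its participants.

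The mismatch stands, and so does the point that the documents do not resolve it. The consequences do not follow. The target is not ambiguous: 40 is the only accrual figure, stated under its own label and then repeated, and a count in a product description does not compete with it. The worry about Aim 2 supposes people enrolled without a device, which the Protocol does not allow. A shortage would mean fewer participants, not participants with missing exposure.

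The possible edits gain little. Correcting the count or naming a further source leaves every analysis as it is. Cutting accrual to 20 would give up half of a small study to match a number that may simply be out of date, which is a poor trade.

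**Conclusion.** The discrepancy is genuine but clerical: 20 devices counted against at least 40 needed, a gap of 20. It does not warrant a change to the plan. Device supply is a practical matter that the study team must settle before each participant is given a headband. If the plan is followed, with 40 participants each holding a device, the estimates and intervals are unaffected.

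This rests on two readings of the text. The first is that twenty is not presented as the total supply. The second is that 40 is the operative target, as its two statements indicate. If supply did turn out to cap enrolment at 20, standard errors for a simple mean would be 1.41 times those at 40, but the documents do not show that this will happen. Even then the effect would be wider intervals in an exploratory study, and the shortfall would be plain from the number enrolled.

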#### **Subject Retention:**

Participants will not be remunerated for participating in this study, but they will be allowed to keep the Muse-S™ Headbands.

#### **Resources:**

- The data entry screens used will be developed via REDCap for the online forms.
- Clinician investigators will provide medical oversight.
- The Muse-S™ Headband systems are provided at no cost through the manufacturer (InteraXon) for use during study participation.

Check all that apply. If none apply, leave blank:

The research involves contact or interaction with subjects, for example, surveys, questionnaires, observation, blood draw.

#### **Study Design:**

We will use standardized procedures to ensure uniform instructions and support for all subjects for the recruitment, screening, and study entry.

#### Recruitment:

HCP participants will be recruited from the Mayo Clinic Practice. The study staff will inform participants of the study during practice meetings, and if the participants indicate interest they will connect with research staff and arrange a time to meet to begin the consent process.

Participants will not be reimbursed for their time spent in the study, but all participants will be given the option of keeping the Muse-S™ Headband system for continued use post study participation.

#### Consent and Screen:

Study coordinator will meet with the potential participant who has expressed an interest in participating in the study. The study coordinator will begin by introducing the study details, and after determining that the subject has continued interest in study participation, will move on to the study consent. If the subject

chooses to consent, the study coordinator will screen the participant for study entry inclusion/exclusion criteria. If the study entry criteria are met, the subject will begin their study participation. They will be asked to complete the study surveys/questionnaires.

*Please note:* Participants must have access to an iOS or Android capable device to take part in this study in order to interact with the Muse-S™ Headband system.

Treatment phase:

During the first three months of study, participants will be asked to complete the online study intervention using the Muse-S™ headband. Participants will be contacted via telephone and online (REDCap) for study visits at day 14 and 30. At day 90, they will be asked to return to the clinic for an in-person visit (telephone and online will be alternatives).

Study Follow-Up Visits:

The study will consist of a 6-month visit post baseline (3-month post end of intervention). Participants will be asked to complete an in-person visit, if possible (telephone and online will be the alternative).

